8.3 Masking/Blinding of Study

This is an open-label pilot investigation. Masking and blinding procedures are not applicable.

9 Study Procedures

9.1 Visit 1 (Screening and Enrollment up to the day of surgery)

- Review of medical record
- Informed Consent Patients will be identified during their preoperative appointment and introduced to a study; they will be provided with a copy of the consent document and information about the study. The consenting will take place after additional discussion on the day of surgery.

9.2 Visit 2 (Randomization and Treatment – day of surgery)

- Elective surgical procedure as in which intraoperative access to the arms is restricted because of surgical draping.
- Anesthetic management will be standardized to utilize rocuronium, sevoflurane, and sugammadex or neostigmine at the discretion of the attending anesthesiologist
- Prior to induction of anesthesia, the Tetragraph electrodes will be placed over the ulnar nerve and the thumb to measure the response of adductor pollis nerve. Randomization will be performed utilizing REDCap and involves the use of dominant vs non-dominant arm.

• Following induction of anesthesia but prior to NMBA administration, baseline values will be recorded from both monitors after calibration.

- Anesthesia providers will have access to the TetraGraph and TOFScan values during the
 entire procedure, and will make clinical decisions as per usual clinical routine at Mayo
 Clinic.
- After NMBA administration, sets of measurements will be taken with the two monitors at regular intervals (every 12 sec, 20 sec, 1 min, 15 min, etc.) as required per usual clinical routine and determined by the anesthesia attending.
- Near the conclusion of the operation but prior to the reversal of neuromuscular block, another set of measurements will be taken, with the two monitors, as per usual clinical routine, in order to determine the appropriate reversal drug dosage.
- After sugammadex or neostigmine administration, measurements will be taken every 20 seconds until return of neuromuscular function is documented.
- Following documentation of adequate neuromuscular function (TOF ratio is >0.9,) the devices will be removed and the patient will proceed along the standard recovery pathway.

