The original System Usability Scale (SUS) was developed by John Brooke in 1986 (https://www.usabilitest.com/system-usability-scale), and it allows investigators to evaluate a wide variety of products and services, including hardware, software, mobile devices and websites. It is a simple, ten-item Likert scale with five response options for respondents; the responses vary from "Strongly agree" to "Strongly disagree." The scale provides a quick and reliable tool for measuring the usability of the product in question.

The usability of the two monitors will be determined throughout various stages of neuromuscular blockade, including onset of blockade following neuromuscular relaxant administration, maintenance, and reversal of blockade with sugammadex or neostigmine until adequate recovery (train-of-four ratio >0.9) is confirmed. At the end of each surgical case, the healthcare provider will be asked to rate the usability of the TetraGraph and the usability of the TOFScan monitors based on the ten items on the SUS scale.

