6.4 Primary Study Endpoints

The primary endpoint of the study will be to determine the usability of the two monitors using the SUS Plus scale.

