8.2 Method for Assigning Subjects to Treatment Groups

This is an open-label investigation and all study participants are assigned to both TetraGraph and TOFScan devices. The randomization involves the use of dominant vs non-dominant arm for the placement of TetraGraph device.

The randomization will be performed utilizing REDCap and assigned anesthesia clinical care team will be informed of patients' assigned to guide them with the selection of the assigned treatment option.

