18.3 Tetragraph SUS

Question			R	ating			
I think that I would like to use TetraGraph		1	2	3	4	5	
frequently.	Strongly Disagree	0	0	0	0	0	Strongly Agree
I found TetraGraph unnecessarily complex.		1	2	3	4	5	
Tround TetraOraph unnecessarily complex.	Strongly Disagree	0	0	0	0	0	Strongly Agree
		1	2	3	4	5	
I thought TetraGraph was easy to use.	Strongly Disagree	0	0	0	0	0	Strongly Agree
I think that I would need the support of a		1	2	3	4	5	
technical person to be able to use TetraGraph.	Strongly Disagree	0	0	0	0	0	Strongly Agree
I found the various functions in TetraGraph		1	2	3	4	5	
were well integrated.	Strongly Disagree	0	0	0	0	0	Strongly Agree
I thought there was too much inconsistency in		1	2	3	4	5	
TetraGraph.	Strongly Disagree	0	0	0	0	0	Strongly Agree
I would imagine that most people would learn		1	2	3	4	5	
to use TetraGraph very quickly.	Strongly Disagree	0	0	0	0	0	Strongly Agree
		1	2	3	4	5	
I found TetraGraph very cumbersome to use.	Strongly Disagree	0	0	0	0	0	Strongly Agree
I folk and a second flow to a second flo		1	2	3	4	5	
I felt very confident using TetraGraph.	Strongly Disagree	0	0	0	0	0	Strongly Agree
I needed to learn a lot of things before I could		1	2	3	4	5	
get going with TetraGraph.	Strongly Disagree	0	0	0	0	0	Strongly Agree

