18.4 TOFScan SUS

Question			R	ating			
I think that I would like to use TOFScan		1	2	3	4	5	
frequently.	Strongly Disagree	0	0	0	0	0	Strongly Agree
		1	2	3	4	5	
I found TOFScan unnecessarily complex.	Strongly Disagree	0	0	0	0	0	Strongly Agree
I d. Torg		1	2	3	4	5	
I thought TOFScan was easy to use.	Strongly Disagree	0	0	0	0	0	Strongly Agree
I think that I would need the support of a		1	2	3	4	5	
technical person to be able to use TOFScan.	Strongly Disagree	0	0	0	0	0	Strongly Agree
I found the various functions in TOFScan were		1	2	3	4	5	
well integrated.	Strongly Disagree	0	0	0	0	0	Strongly Agree
I thought there was too much inconsistency in		1	2	3	4	5	
TOFScan.	Strongly Disagree	0	0	0	0	0	Strongly Agree
I would imagine that most people would learn		1	2	3	4	5	
to use TOFScan very quickly.	Strongly Disagree	0	0	0	0	0	Strongly Agree
		1	2	3	4	5	
I found TOFScan very cumbersome to use.	Strongly Disagree	0	0	0	0	0	Strongly Agree
		1	2	3	4	5	
I felt very confident using TOFScan.	Strongly Disagree	0	0	0	0	0	Strongly Agree
I needed to learn a lot of things before I could get going with TOFScan.		1	2	3	4	5	

Strongly Disagree OOOOO Strongly Agree

19 List of In-Text Figures

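### Neither SUS form order nor monitor set-up order is controlled or recorded, so an order effect could be mixed with the device difference in the primary comparison

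*Combined protocol and SAP*

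**What the plan says.** The primary endpoint (6.4) is usability: "The primary endpoint of the study will be to determine the usability of the two monitors using the SUS Plus scale". The comparison is made within each case, since "all study participants are assigned to both TetraGraph and TOFScan devices" (8.2). The one randomised element is the arm: "The randomization involves the use of dominant vs non-dominant arm for the placement of TetraGraph device" (8.2, repeated in 9.2). The study is open-label (8.3).

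On set-up, 9.2 states "Prior to induction of anesthesia, the Tetragraph electrodes will be placed over the ulnar nerve and the thumb". It gives no placement time for TOFScan. The only later limit is that, after induction and before the neuromuscular blocking agent, "baseline values will be recorded from both monitors after calibration".

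On rating, 4.1 says that at the end of each case "the healthcare provider will be asked to rate the usability of the TetraGraph and the usability of the TOFScan monitors". The two ten-item forms are printed as "18.3 Tetragraph SUS" and then "18.4 TOFScan SUS".

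Section 10.2.1 says that SUS will be compared between the monitors but names no test, model or order term. Table 18.2 has columns for arm and for time, with one time column shared by both monitors. It has no item for which monitor was set up first or which form was completed first.

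**The concern.** Two things can happen first or second in each case: setting up a monitor and filling in its form. Randomising the arm balances hand dominance between devices. It does nothing for either order.

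A rater who has just scored one monitor may score the next by comparison with it, and the two set-ups may not take place under the same conditions. Suppose one device nearly always comes first. The average SUS difference then estimates the device effect plus the order effect, and enrolling more patients does not separate them. If the order varies but is not recorded, it cannot be adjusted for. Set-up order could in principle also bear on the secondary endpoint in 6.5, failure to calibrate and measure, because both calibrations fall between induction and the blocking agent.

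**Working it through.** **The plan's own figure.** Section 10.1 gives 23 patients for 90% power by a paired t-test on TOF ratio, with SD 0.07 and significance level 0.05. It does not state the difference to be detected. Solving backwards with a two-sided test gives 0.0495. With an assumed difference of 0.05, the calculation returns n = 23 with power 90.5%. This figure concerns TOF ratio, so it says nothing about SUS or about order. Enrolment is 3 × 35 = 105.

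**Inputs for the illustration.** From the documents: n = 105 cases, two ratings per case, significance level 0.05. Assumed, because the documents do not give them:
- an order shift s of 2 to 5 SUS points;
- an SD of 15, 20 or 25 points for the within-case difference;
- independent ratings;
- a two-sided paired t-test;
- the same device first in every case;
- no true device difference.

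**Formula.** Noncentrality = (s / SD) × √n, with √105 = 10.247. The critical t on 104 df is 1.983. The chance of p<0.05 is the noncentral-t probability beyond ±1.983.

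For SD 20, the noncentralities are:
- s = 2: 0.10 × 10.247 = 1.02
- s = 3: 0.15 × 10.247 = 1.54
- s = 4: 0.20 × 10.247 = 2.05
- s = 5: 0.25 × 10.247 = 2.56

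| SD of difference | s = 2 | s = 3 | s = 4 | s = 5 |
|---|---|---|---|---|
| 15 | 27% | 53% | 77% | 92% |
| 20 | 17% | 33% | 53% | 72% |
| 25 | 13% | 23% | 37% | 53% |

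Without an order effect every cell would be 5%.

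**If the order is not constant.** Let q be the share of cases with TetraGraph first, and let the effect reverse sign when TOFScan is first. The bias is then q × s − (1 − q) × s = (2q − 1) × s. With q = 1 and s = 4 it is 4 points. With q = 0.75 it is 0.5 × 4 = 2 points. With q = 0.5 it is 0. The table is therefore the worst case for each shift.

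**If form order is balanced.** In simulation (104 pairs, 52 in each order, SD 15 or 20, shifts of 2, 3 and 5 points, 20,000 trials each), the mean estimate lay between −0.01 and 0.03 points. The order-adjusted test rejected in 4.7% to 5.2% of trials. The cost in precision is small even without adjustment: a 4-point effect raises the SD from 20 to √(20² + 4²) = √416 = 20.4. An odd 35 per centre can split 18 to 17, which leaves (18 − 17)/35 = 0.029 of the shift. For a 5-point shift that is 5 × 0.029 = 0.14 points before adjustment.

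**The case against.** The strongest reply is that nothing in the plan fixes either order.

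- **Form order.** The rating sentence in 4.1 joins the two devices with a plain conjunction, and table numbers are not a sequence of administration. The aim sentence in the same section names TOFScan first, and the objective in the study summary puts AMG before EMG. The forms are held in REDCap (12.3, 12.4), whose screen order is not shown.
- **Set-up order.** Section 9.2 does not say that TOFScan goes on second or after induction. Calibration and baseline share one window for both monitors.
- **Direction.** TOFScan is already in routine use at the lead institution (8.1), and familiarity could outweigh any effect of sequence.
- **Size.** The shift and the SD are both assumed. Set-up and form effects are different mechanisms and could cancel. The documents do not say whether one provider may rate several cases, and the plan names no test for SUS.
- **Cost.** This is an open-label study that calls itself a pilot. A prescribed set-up sequence at three centres would burden staff and create deviations.

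Most of this stands. A reader might infer that the TetraGraph form must be completed first, that TOFScan is set up second under more time pressure, or that the bias is certain and no analysis could remove it. The documents support none of these. The full one-for-one bias needs a constant order; with a varying, recorded order it is smaller and can be adjusted for.

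What the reply does not remove is the gap itself. Both orders are left uncontrolled and unrecorded, and the protocol's procedural cues all point the same way. The REDCap audit trail would not settle form order, because 12.4 describes transcription from source documents, so entry order need not be answering order.

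**Conclusion.** The point holds as a risk to the primary comparison that is cheap to remove. It is not a demonstrated bias. If TetraGraph is consistently first, any first-versus-second effect is mixed with the device difference on an unmasked rating scale. The size and direction of such an effect cannot be taken from the documents.

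The range of 17% to 72% describes a hypothetical: one device always first, 105 independent ratings, a paired t-test, SD 20 and a shift of 2 to 5 points. It should not be read as this trial's false-positive rate. With SD 15 the range is 27% to 92%, and with SD 25 it is 13% to 53%. A less constant order lowers all of these figures.

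The two orders deserve different treatment. Form order is not a property of either device, and randomising it costs almost nothing. For set-up, the documents do not make a case for imposing a randomised sequence on staff. A common placement window and a record of what was done are enough.

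**What to change.** 1. In 8.2, add to the existing REDCap randomisation which SUS form is shown first, 1:1 within centre. If the forms are answered on paper and transcribed, the paper pack must follow the allocated order.
2. In 10.2.1, state a paired analysis of SUS with form order as a term.
3. In 9.2, state one placement window common to both monitors. Its timing is for the study team to choose.
4. In Table 18.2, record which monitor was set up first and which was calibrated first. Use this in a sensitivity analysis of SUS and of failure to calibrate.

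The cost is one more allocation field, one more CRF item and one degree of freedom in the model. Form order can be balanced only for cases not yet enrolled, so the change is best made before recruitment starts.

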9.3 Schedule of Events

	Schedule of Events						
Study Activity	Visit 1	Visit 2					
Tetragraph		X					
TOFScan		X					
Informed consent	X						
Review of Medical Record	X						
Adverse event evaluation		X					

10 Statistical Plan

10.1 Sample Size Determination

Based on paired t-test, 23 enrolled patients will give 90% power to detect a difference in TOF ratios with a significance level of 0.05 (JMP Pro Software version 13.0.0

[August 23, 2018]; SAS Institute Inc., Cary, NC). We utilized a standard deviation of 0.07 that was determined during our multi-center volunteer study comparing another AMG device and TetraGraph. However, each participating center will enroll 35 patients to take into account

patient loss or missing data. The total number of patients for this study from all 3 centers will be aimed at 105 participants.

10.2 Statistical Methods

10.2.1 Descriptive Statistics

Analysis of agreement between the two monitors will be assessed using Bland-Altman. The limits of agreement are defined as bias \pm 2 SD, where SD denotes the standard deviations of the differences. Limits of agreement are interpreted as the reference range within which 95% of the differences will lie. The bias and the limits of agreements surrounding the bias (\pm 2 SD) will be calculated with 95% confidence intervals. Statistical significance will be defined as a p-value <0.05. Comparison of the usability of the two monitors will be made using the System Usability Scale (SUS) Plus. The SUS is particularly relevant to user experience when comparing two monitors that are based on different technologies (AMG and EMG). It will allow us to make a comparison of the two monitors in a surgical setting in which access to the monitoring muscle site (the thumb and hand) is limited. Because SUS is technology-neutral, we will be able to continue to use it in usability testing as technology evolves over the years, allowing us to continually evaluate and select the optimal monitoring technology available.

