6.3 Duration of Participation

2-5 hours, depending on duration of surgery

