10.3 Subject Population(s) for Analysis

Each participant who goes through the surgery and completes monitoring of residual neuromuscular blockade will be included in the primary analysis regardless of study withdrawal for any reason. In the event of any study withdrawals, in secondary analysis we will examine the sensitivity of our results to the exclusion of patients who withdraw.

11 Safety and Adverse Events

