18.2 Intraoperative Data

•		Date of Surgery (dd / mm / yyyy):		Examiner's Initials:		
Wrist circumference (right):		Wrist circumference (left):		Dominant side: L / R		
Ankle circumference (right):		Ankle circumference (left):				
Age (yrs):	Weight	(kg):		Height (cm):		BMI:
Muscle relaxant name	:					
Muscle relaxant total dose (mg):						
Time of first muscle re	elaxant	dose (mm :	: hh):		:	am / pm

Reversal agent name:					
Reversal agent dose (mg)	:				
Time of reversal agent administration (mm : hh):				:	am / pm
Time of extubation:		:		am / pm	

TetraGraph (TG) / TOFScan

	Time	TetraGraph (TG) Arm L/R	TOFScan Arm L / R	TOFR # 3 (if needed)
Calibrated baseline TOFR and supramax current				
TOFC=0 (post initial dose of NMBA)				
Time Interval (first recheck)				
Time Interval (second recheck)				
Time Interval				
Time Interval				
Time Interval				

Time Interval		
Time Interval		

Time Interval		
pre-SGX		
+60sec after SGX		
+120 sec after SGX		
+180 sec after SGX		
+260 sec after SGX		
Extubation		
Time to recovery following SGX (TOFR ≥0.9)		
T0 (on arrival to PACU)		
T5 (5 min after PACU arrival)		
T10 (10 min after PACU arrival)		

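### The Bland-Altman rule in 10.2.1 assumes independent differences, but several pairs per patient are planned and nothing says which enter or how clustering by patient is handled

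*Combined protocol and SAP*

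**What the plan says.** **The rule.** Section 10.2.1 assesses agreement by Bland-Altman. The limits are bias ± 2 SD, "where SD denotes the standard deviations of the differences", and the bias and limits get 95% confidence intervals. No interval formula is given.

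**The readings.** Every patient wears both monitors (8.2). Section 9.2 records a baseline. After the blocking agent, "sets of measurements will be taken with the two monitors at regular intervals (every 12 sec, 20 sec, 1 min, 15 min, etc". The spacing is not fixed by the protocol; readings are made "as required per usual clinical routine and determined by the anesthesia attending". There is another set before reversal. After reversal, "measurements will be taken every 20 seconds until return of neuromuscular function is documented". The form in Table 18.2 has columns for both devices and rows for baseline, repeated rechecks (such as "Time Interval (second recheck")), pre-reversal, four post-reversal times, extubation and three PACU times. Participation lasts "2-5 hours, depending on duration of surgery" (6.3).

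**What bears on the unit of analysis.** Section 10.1 says: "Based on paired t-test, 23 enrolled patients will give 90% power to detect a difference in TOF ratios". Section 10.3 says: "Each participant who goes through the surgery and completes monitoring of residual neuromuscular blockade will be included in the primary analysis". That defines the patients analysed, not the readings. Section 4.2 names onset, maintenance and reversal as the periods of interest, without linking them to the Bland-Altman analysis.

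**The concern.** Readings from the same patient share that patient's arm, electrode placement and device offset, so their differences are likely to be correlated. A plain SD divided by the square root of the number of pairs ignores this and gives intervals that are too short. Because the number of pairs varies with case length, the attending's choice of interval and recovery time, pooling would also give more weight to patients with more readings.

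The TOF-ratio comparison is part of the primary objective (section 5) and is the only outcome used for sample size (10.1). Bland-Altman is the only method named for it. At stake are the stated precision of the agreement result and a choice of unit that could be made after the data are seen.

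**Working it through.** **1. The plan's own figure.** Section 10.1 gives 23 patients, 90% power, significance level 0.05 and SD 0.07, but no difference to detect. The figure therefore cannot be reproduced from stated inputs. Solving backwards with the noncentral t (two-sided), n = 23 implies a difference of 0.0495. An assumed difference of 0.05 needs exactly 23 patients (power 90.5%). So 23 fits one difference per patient, but neither the difference nor the reading is stated.

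**2. Inputs for the pooled case.**
- N = 105 patients (6.2, 10.1).
- SD = 0.07 (10.1). It comes from a volunteer study of another AMG device and is not stated to be an SD of paired differences.
- Pairs per patient, m: assumed. Table 18.2 has 7 rows likely to hold a ratio outside the interval and PACU rows: 1 baseline + 1 pre-reversal + 4 post-reversal + 1 extubation. Five allows for early device removal. Unequal numbers are taken as uniform on 2-8 (mean 5, mean square 29) and 2-12 (mean 7, mean square 59).
- Within-patient correlation of the differences, ρ = 0.1, 0.3, 0.5: assumed, since the documents give no value.

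**3. Interval for the bias.** Design effect D = 1 + (E[m²]/E[m] − 1)ρ, which is 1 + (m − 1)ρ for equal m. Plain half-width = 1.96 × 0.07/√(105 × mean m). Correct half-width = plain × √D. Actual coverage = 2Φ(1.96/√D) − 1.

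Example, m = 5 and ρ = 0.3: D = 1 + 4 × 0.3 = 2.2 and √D = 1.48. The plain half-width is 1.96 × 0.07/√525 = 0.0060, the correct one is 0.0089, and coverage is 2Φ(1.32) − 1 = 81%.

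| Pairs per patient | D at ρ = 0.1/0.3/0.5 | Plain half-width | Correct half-width | Coverage |
|---|---|---|---|---|
| 5 | 1.40/2.20/3.00 | 0.0060 | 0.0071/0.0089/0.0104 | 90/81/74% |
| 7 | 1.60/2.80/4.00 | 0.0051 | 0.0064/0.0085/0.0101 | 88/76/67% |
| 2-8 | 1.48/2.44/3.40 | 0.0060 | 0.0073/0.0094/0.0110 | 89/79/71% |
| 2-12 | 1.74/3.23/4.71 | 0.0051 | 0.0067/0.0091/0.0110 | 86/72/63% |

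More pairs lower coverage further: at m = 10 and ρ = 0.5, D = 5.5 and coverage is 60%.

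**4. Interval for the upper limit.** With s the pooled SD, Var(limit) = Var(bias) + 4Var(s), and Var(s) is taken from the between- and within-patient variance components. At m = 5 and ρ = 0.5 the half-width is 0.0104 by the plain rule and 0.0159 allowing for clustering. Simulated coverage (normal data, 4000 runs per cell) is 93/87/80% at 5 pairs and 92/83/74% at 7.

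**5. What does not change.** The mean pooled SD in simulation is 0.0697 to 0.0700 in all these cases, so the limits stay at about ± 2 × 0.07 = ± 0.14. With one pair per patient, coverage is about 95% for both the bias and the limit, and the rule is correct.

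**6. Reading times.** After reversal, 9.2 implies 260/20 = 13 readings in 260 seconds. Table 18.2 has four rows in that span, at 60, 120, 180 and 260 seconds. The two therefore do not settle how many pairs there are.

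**The case against.** The strongest reply is that the error is conditional. A reader might infer that the plan pools all readings, but no section says so. The only statistical text that implies a unit is the paired t-test in 10.1, sized in patients, and with one difference per patient the plain-SD rule is right. This stands, and it is why every coverage figure above is conditional. It does not close the gap, because 10.1 names neither a time point nor a summary. Section 3 also puts repeatability in the primary aim, which suggests that the repeated readings are meant to be used.

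A reader might also infer that no time points exist at all, or that 9.2 and Table 18.2 flatly contradict each other. Neither is supported. Section 4.2 names three phases, and 8.1 says TetraGraph data are stored on its SD card and downloaded later, so the form rows may be a selection from denser capture. What is missing is which readings the analysis uses.

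The consequence is also limited. The named primary endpoint is the SUS score (6.4) and the secondary endpoint is failure frequency (6.5); neither uses Bland-Altman. The method sits under descriptive statistics in a study that calls itself a pilot (8.3, 10.2.2), and no margin or decision depends on the limits. All of this stands and limits the weight of the point.

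**Conclusion.** The plan gives one agreement rule, suited to independent differences, alongside a design that yields several correlated pairs per patient. It leaves the unit, the readings and the clustering unstated. If the repeated pairs enter the rule, a nominal 95% interval for the bias covers about 86-90%, 72-81% and 63-74% at correlations of 0.1, 0.3 and 0.5. This rests on 105 patients, SD 0.07, a mean of 5 to 7 pairs and normal differences. The correlations and pair counts are assumptions, and the SD carries the caveat above.

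In absolute terms the half-width for the bias grows by about 0.001 to 0.006, beside limits of about ± 0.14. The harm is overstated precision and an analysis choice left open. It would be wrong to conclude that the limits are biased to any material degree, or that the SUS result is at risk. The point should be fixed before analysis, but it does not threaten the trial's main endpoint.

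**What to change.** Add to 10.2.1, in substance:

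> Agreement in TOF ratio is analysed on paired readings nested in patient, separately for onset, maintenance and reversal, with the readings in each phase listed. Bias and limits come from a model for the paired difference with a random patient effect; limits = bias ± 2 × √(between-patient + within-patient variance). The 95% confidence intervals are obtained by resampling patients. Intervals for any TOFC or PTC comparison also resample patients.

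In simulation with normal data (5, 7, 2-8 or 2-12 pairs, with and without serial correlation), this method covered 93-96% for the bias and 91-95% for the upper limit. TOF ratio is bounded and has no value when the fourth response is absent, so performance within each phase should be checked. If the number of readings is related to a patient's difference, the model reduces the resulting shift in the bias but does not remove it.

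Alternatively, name one pair per patient and keep the plain-SD rule. The pair can be a single time point or a patient mean; a patient mean gives limits for means, not for single readings.

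In either case, reconcile the post-reversal reading times in 9.2 with the rows in Table 18.2, since they determine the number of pairs.

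The cost is a few sentences, modest programming and somewhat wider intervals. No new data are needed.
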